**Table 18 Guidelines for Management of Hematologic Toxicities That Occur on Days 8 and 15 of Cycle 1**

Event	Action to Be Taken
Febrile neutropenia or neutropenia with infection	
 
• Withhold obinutuzumab until resolution of fever and infection (as applicable).
 
• If the event is ongoing on Day 1 of Cycle 2, follow instructions in Table 17.
 
 
Note: Obinutuzumab should not be withheld for asymptomatic neutropenia.

Severe thrombocytopenia a or bleeding	
 
• Withhold obinutuzumab until platelet count <math>\geq 50,000/\mu\text{L}</math> and resolution of bleeding.
 
• If the event is ongoing at Day 1 of Cycle 2, follow instructions in Table 17.
 

a Severe thrombocytopenia is defined as a platelet count  $< 10,000/\mu\text{L}$  for patients who are not receiving concomitant anticoagulants or platelet inhibitors.

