### **4.6.2 Study Treatment Discontinuation**

Study treatment (obinutuzumab *or rituximab* and idasanutlin) should be permanently discontinued in patients who experience any of the following:

- DLT during *the DLT window* in patients enrolled in the dose-escalation phase
- Anaphylaxis, acute respiratory distress, or Grade 4 IRR
  - If a Grade 3 IRR is recurrent during the second and subsequent cycles, study treatment may be discontinued at the discretion of the investigator, following an individual benefit• risk assessment.
- Any adverse event that leads to a delay of more than 21 days in the start of the next treatment cycle
- Any hematologic adverse event that meets criteria for permanent discontinuation per guidelines provided in Section 5.1.5
- Grade • 3 non-hematologic adverse event that has a reasonable possibility of being related to study treatment and is either life threatening or does not resolve to Grade <2 within 21 days
- Disease progression
- Pregnancy

The primary reason for study treatment discontinuation should be documented on the appropriate eCRF.

Patients who discontinue study treatment will not be replaced, except as outlined below:

- During the dose-escalation phase (Part 1), patients who discontinue study treatment prior to completing Cycle 1 for reasons other than toxicity will be replaced.
- Patients discontinued before having received at least one dose of each component of the combination will be replaced.

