### 5.1.5.1 Toxicities during Induction Treatment Hematologic Toxicities

Table 17 provides guidelines for management of hematologic toxicities that occur during induction treatment, with the exception of Days 8 and 15 of Cycle 1. Table 18 provides guidelines for management of hematologic toxicities that occur on Days 8 and 15 of Cycle 1, when patients are to receive treatment with obinutuzumab only. Hematologic toxicity is defined as neutropenia, anemia, or thrombocytopenia. Lymphopenia is not considered hematologic toxicity but an expected outcome of therapy.

**Table 17 Guidelines for Management of Hematologic Toxicities That Occur during Induction Treatment (Except for Days 8 and 15 of Cycle 1)**

Event	Action to Be Taken

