Grade 3 or 4 hematologic toxicity a, b	
For patients who have had one, two, or no prior dose reductions:
 
 
• Withhold study treatment.a
 
• Administer RBCs or platelets as required.
 
• If patient has not already initiated G-CSF, initiate prophylactic G-CSF for current and subsequent cycles.
 
• If improvement to Grade • 2 or baseline • 14 days after the scheduled date for the next cycle, resume obinutuzumab or rituximab at full dose and resume idasanutlin at current dose.
 
• If improvement to Grade • 2 or baseline 15• 21 days after the scheduled date for the next cycle, resume obinutuzumab or rituximab at full dose and resume idasanutlin at a reduced dose according to guidelines in Section 5.1.5 for current and subsequent cycles.
 
• If study treatment is withheld for >21 days, permanently discontinue study treatment.
 
• Permanently discontinue study treatment if any of the following events occur: 
 
Grade 3 or 4 thrombocytopenia of any duration if associated with Grade ≥ 3 bleeding
 
Recurrent Grade 3 or 4 neutropenia associated with fever of > 38°C (> 5 days) or a documented infection despite use of G-CSF and after one idasanutlin dose reduction
 
Recurrent Grade 4 neutropenia or thrombocytopenia lasting more than 7 days despite use of G-CSF (for neutropenia) and after one idasanutlin dose reduction
 
 
 
 
For patients who have had three prior dose reductions or for patients who reach the lowest dose level and no further dose reduction is applicable (see Section 5.1.5):
 
 
• Permanently discontinue study treatment.
 

G-CSF = granulocyte colony-stimulating factor; NHL = non-Hodgkin's lymphoma.

a Treatment delays apply to all toxicities; dose modifications apply only to toxicities that are considered to be related to idasanutlin

b If cytopenia is thought to be caused mainly by NHL infiltration of the bone marrow, the investigator may decide not to modify dose.

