**Table 19 Guidelines for Management of Non-Hematologic Toxicities (cont.)**

Event		Action to Be Taken
		taking idasanutlin and all expelled tablets are still intact, another dose may be given and the second dose noted in the drug log. Otherwise, no replacement dose is to be given.
Dermatologic toxicity		Permanently discontinue rituximab in the event of Stevens-Johnson syndrome or toxic epidermal necrolysis.
Other non-hematologic toxicities (i.e., not described above), excluding alopecia, nausea, and vomiting	Grade 3 or 4	
For patients who have had no prior dose reductions:
 
 
Withhold study treatment.a
 
If improvement to Grade • 1 or baseline, resume obinutuzumab or rituximab at full dose and resume idasanutlin at a reduced dosea for current and subsequent cycles according to guidelines in Section 5.1.5 for current and subsequent cycles.
 
 
For patients who have had one prior dose reduction:
 
Grade 4 events
 
 
Permanently discontinue study treatment.
 
 
Grade 3 events
 
Withhold study treatment.a
 
 
If improvement to Grade • 1 or baseline, resume obinutuzumab or rituximab at full dose and idasanutlin at a reduced dose according to guidelines in Section 5.1.5 for current and subsequent cycles.
 
 
For patients who have had two prior dose reductions or for patients who reach the lowest dose level and no further dose reduction is applicable (See Section 5.1.1.5):
 
Permanently discontinue study treatment.

	Grade 2	
 
Withhold study treatment.a
 
If improvement to Grade • 1 or baseline, resume obinutuzumab or rituximab at full dose and idasanutlin at current dose
 

h = hour; IRR = infusion-related reaction; PML = progressive multifocal leukoencephalopathy; QD = once a day; TLS = tumor lysis syndrome; ULN = upper limit normal.

a Treatment delays apply to all events; dose modifications apply only to events that are considered to be related to any of the study treatment components. Toxicities that occur during the cycle and subside prior to the next cycle should not trigger the suggested dose modifications.

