**Table 20 Guidelines for Management of Toxicities That Occur during Maintenance Treatment**

Event	Action to Be Taken
Hematologic toxicity: Grade 3 or 4	

• Withhold study treatment.

• Administer myeloid growth factors for neutropenia as allowed according to institutional guidelines.

• If improvement to Grade • 2, resume obinutuzumab or rituximab at full dose and idasanutlin at reduced dose.

• If study treatment is withheld for >42 days, permanently discontinue.

Non-hematologic toxicity: Grade • 2	

• Withhold study treatment

• If improvement to Grade • 1 or baseline, administer obinutuzumab or rituximab at full dose and idasanutlin at reduced dose.

• If study treatment is withheld for >42 days, permanently discontinue.

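### For expansion FL patients, Table 18 lets treatment resume after a thrombocytopenic Grade 3 bleed on Cycle 1 Day 8 or 15, an event that Table 17 makes a permanent stop on every other induction day

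*Combined protocol and SAP*

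**What the plan says.** Four places in the protocol bear on this event.

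- **Table 17 (Section 5.1.5.1)** lists events that permanently end study treatment. One is Grade 3 or 4 thrombocytopenia "of any duration if associated with Grade ≥ 3 bleeding". The lead-in limits the table to induction "with the exception of Days 8 and 15 of Cycle 1".
- **Table 18 (Section 5.1.5.1)** covers those two days. For severe thrombocytopenia or bleeding it says "Withhold obinutuzumab until platelet count" reaches 50,000/µL and bleeding has resolved. It names no bleeding grade and no permanent stop, and refers to Table 17 only if the event is still present at Cycle 2 Day 1.
- **Section 4.6.2** has two relevant general rules. The hematologic rule stops treatment for "Any hematologic adverse event that meets criteria for permanent discontinuation per guidelines provided in Section 5.1.5". The non-hematologic rule covers a Grade 3 or higher event that may be related and "is either life threatening or does not resolve to Grade <2 within 21 days".
- **Sections 3.1.2, 3.1.2.1 and 4.6.2** make the same event a DLT and a permanent stop, but only for dose-escalation patients within the DLT window.

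For post-induction treatment, Table 20 has no bleeding criterion. After Grade 3 or 4 hematologic toxicity it reads "If improvement to Grade • 2, resume obinutuzumab" or rituximab at full dose, with idasanutlin reduced. A hold of more than 42 days is its only permanent stop.

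**The concern.** Table 17's wording makes duration irrelevant: once thrombocytopenia comes with a bleed of Grade 3 or worse, recovery does not bring the patient back to treatment. Table 18 works the other way, since recovery is exactly what allows the next infusion. Read literally, the same event ends treatment on Day 7 or Day 9 and is held and resumed on Day 8. The protocol gives no reason for the exemption.

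The two exempt days are obinutuzumab infusion days. Section 5.1.1.4 describes acute thrombocytopenia within 24 hours of infusion and, in CLL patients, fatal hemorrhage in Cycle 1, while stating that no clear relationship between the two has been established. In Regimen A the patient has also just taken idasanutlin on Days 1 to 5. At stake is whether the sponsor's own stopping rule protects expansion patients consistently.

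**Working it through.** The documents give no figure to reproduce, so the check traces one event through each rule and then sizes the exposure.

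**Event traced:** Grade 3 or 4 thrombocytopenia with a treatment-related, non-life-threatening Grade 3 bleed that resolves before Cycle 2 Day 1.

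| Setting | Governing rule | Result |
|---|---|---|
| Dose escalation, DLT window | 3.1.2, 3.1.2.1, 4.6.2 | Permanent stop |
| Expansion FL induction, any day except Cycle 1 Days 8 and 15 | Table 17 | Permanent stop |
| Expansion FL, Cycle 1 Day 8 or 15 | Table 18 | Hold, then resume |

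**Could another rule catch the third row?**

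1. *Does Table 18's row apply at all?* Its footnote defines severe thrombocytopenia as below 10,000/µL, but the row is triggered by severe thrombocytopenia or by bleeding. Thrombocytopenia above that count with a bleed is inside it.
2. *Hematologic rule in 4.6.2.* It points back to Section 5.1.5. The bleeding criterion exists there only in Table 17, which excludes these days.
3. *Non-hematologic rule in 4.6.2.* The bleed is not life threatening. Cycle 2 Day 1 is scheduled for Day 29, which is 29 − 8 = 21 days after Day 8 and 29 − 15 = 14 days after Day 15. A bleed resolved before then meets the 21-day limit, so no stop follows.
4. *Table 19.* A Grade 3 non-hematologic event is held until Grade 1 or baseline and then treatment resumes. Its footnote adds: "Toxicities that occur during the cycle and subside prior to the next cycle should not trigger the suggested dose modifications".
5. *Table 18's link to Table 17.* It operates only if the event is ongoing at Cycle 2 Day 1.

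None of the five produces a stop.

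**Size of the exposure** (Sections 3.1.3 and 6.1, Table 6)

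- Patients: 40 expansion FL. Expansion DLBCL patients receive rituximab on Day 1 only and are not counted.
- Induction days: 6 × 28 = 168; 2 / 168 = 1.2%.
- Induction obinutuzumab infusions: 3 in Cycle 1 plus 5 on Day 1 of Cycles 2 to 6 = 8; 2 / 8 = 25%.
- Under Regimen B, Cycle 1 is obinutuzumab alone throughout, yet Table 17's stop applies on 28 − 2 = 26 of its 28 days. An obinutuzumab-only period is therefore not in itself the reason for the exemption.

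**What a stop would do to the analysis**

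- Appendix 1 schedules end-of-induction scans only after at least two induction cycles, so a patient stopped in Cycle 1 has none.
- Section 6.4 keeps anyone who received one dose of any component, and Section 6.4.1 counts a patient with no post-baseline assessment as a non-responder. Each such patient can lower the FL CR proportion by at most 1 / 40 = 2.5 percentage points, and only if that patient would otherwise have reached CR.
- Under Regimen B the patient would have had no idasanutlin, and Section 4.6.2 replaces patients discontinued before one dose of each component.

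**The case against.** **Safeguards already exist.** Section 5.2.3 makes Grade 3 or higher thrombocytopenia an event of special interest, reportable to the Sponsor within 24 hours, so every event at issue is reported. Section 4.6.1 lets the investigator withdraw a patient, and Sponsor safety concerns are also grounds; the IMC reviews safety; Appendix 1 requires blood counts within 24 hours before Days 8 and 15. All of this stands and lowers the urgency. These are discretionary or monitoring measures, however, and do not tell a site to stop.

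**Table 18 may be a deliberate rule for obinutuzumab-only days.** Section 5.1.1.4 recommends considering dose delays for severe thrombocytopenia, and Table 18's recovery thresholds are strict. This has some force for Regimen B. It is weaker for Regimen A, where idasanutlin was given earlier in the cycle, and it does not explain why Table 17 governs the other 26 days of a Regimen B Cycle 1.

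**Table 20 is a different case.** A reader might infer that the missing stop there is the same defect. The documents do not support that. Only patients in CR or PR enter post-induction treatment, the antibody is given every 2 months, and Table 20 already requires a lower idasanutlin dose after any Grade 3 or 4 hematologic toxicity. Table 17 by contrast resumes the current dose when recovery comes within 14 days. The omission may be a choice.

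**Other overreadings.** A reader might infer that any serious bleed on Day 8 or 15 can be re-treated, or that dose-escalation patients are exposed. Section 4.6.2 stops related bleeds that are life threatening or slow to resolve, Table 17 takes over for events ongoing at Cycle 2 Day 1, and the DLT rule covers dose escalation.

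**Conclusion.** The inconsistency is real and narrow. For expansion FL patients on two Cycle 1 infusion days, the written rules permit re-treatment after an event that is a permanent stop on the rest of induction, and no other rule forces a stop. It concerns 40 patients, 1.2% of induction days and 25% of induction obinutuzumab infusions. The documents give no rate for thrombocytopenia with Grade 3 or worse bleeding; I assume few events and claim no count.

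The conclusion rests on reading Tables 17 and 18 by the day on which the event occurs, as their titles and lead-in direct, and on a bleed that is related, Grade 3, not life threatening and resolved in time. It does not assume that thrombocytopenia causes the hemorrhage. The gap does not change the planned sample size or any error rate. This is a low-frequency safety-consistency correction that should be made; for Table 20 the documents support only a query.

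**What to change.** In Table 18, add Table 17's permanent stop for Grade 3 or 4 thrombocytopenia "of any duration if associated with Grade ≥ 3 bleeding", and limit the hold-and-resume row to severe thrombocytopenia or bleeding that does not meet that criterion. The dose-delay approach of Section 5.1.1.4 is then kept for thrombocytopenia without a Grade 3 or worse bleed. If the sponsor intends Days 8 and 15 to be handled differently, the protocol should give the reason.

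For Table 20, ask the sponsor whether the same stop is intended while idasanutlin is given with the antibody (6 months), and record the answer.

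The drafting cost is one added line and one qualified row in the next amendment, with no new visits or data collection. The trial cost is that a few patients may stop earlier. Under Regimen B a patient stopped before any idasanutlin is replaced, so an extra patient may be needed; in either regimen a patient stopped in Cycle 1 without a post-baseline assessment counts as a non-responder in the primary analysis.

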### Non-Hematologic Toxicities during Induction Treatment

[Table 19](#) provides guidelines for the management of non-hematologic toxicities that occur during induction treatment.

**Table 19 Guidelines for Management of Non-Hematologic Toxicities**

Event	Action to Be Taken
General guidance for treatment delays and discontinuation	
 
When a treatment cycle is delayed because of toxicity resulting from any component of the regimen, all study treatment should be held and resumed together to remain synchronized.
 
If study treatment is withheld for > 21 days because of a toxicity that is attributable to study treatment, permanently discontinue study treatment.
 

IRRs and anaphylaxis	
 
Guidelines for the management of IRRs and anaphylaxis are provided in Section 5.1.1.1 and Appendix 9.
 
In case of Grade 4 IRRs or anaphylaxis, study treatment should be permanently discontinued.
 

TLS	
 
Withhold study treatment.a
 
Correct electrolyte abnormalities, monitor renal function and fluid balance, and administer supportive care, including dialysis as indicated.
 
If symptoms have resolved completely, resume obinutuzumab or rituximab and idasanutlin at full dose
 

New-onset neurologic manifestations suggestive of PML	
 
Withhold study treatment.a
 
Consult with a neurologist if PML is suspected (refer to Section 5.1.1.5 for guidance on investigations).
 
If PML is ruled out, resume obinutuzumab or rituximab and idasanutlin at full dose.
 
If PML is confirmed, permanently discontinue study treatment.
 

AST, ALT, or bilirubin increase: Grade • 3 (or • 10 • ULN for patients with liver involvement)	
 
Withhold study treatment.a
 
If improvement to Grade • 1 (or ≤ 5 • ULN (Grade 2) for patients with liver involvement), resume obinutuzumab or rituximab and idasanutlin at full dose for current and subsequent cycles.
 
Permanently discontinue study treatment for life-threatening liver toxicity (including Hy's Law cases).
 

**Table 19 Guidelines for Management of Non-Hematologic Toxicities (cont.)**

Event	Action to Be Taken
Diarrhea	
Grade 4 diarrhea: Permanently discontinue study treatment.
 
Grade 2 or 3 diarrhea:
 
 
• If Grade 3 diarrhea occurs between Day 1 and Day 5 of the treatment cycle, withhold study treatment only if diarrhea does not improve to Grade • 2 within 48 hours with appropriate treatment. After dose withheld, if diarrhea improved to Grade • 2, resume obinutuzumab or rituximab at full dose and resume idasanutlin at a reduced dose according to guidelines in Section 5.1.5 for current and subsequent cycles.
 
• If Grade 3 diarrhea is present at the time of the next planned cycle, withhold study treatment. If diarrhea improved to Grade • 2, resume obinutuzumab or rituximab at full dose and resume idasanutlin at a reduced dose according to guidelines in Section 5.1.5 for current and subsequent cycles.
 
 
Management for diarrhea:
 
 
• Initiate treatment at the time of onset.
 
• Administer loperamide 4 mg as loading dose; and up to 2 mg every 4 h or after every unformed stool (for a maximum daily dose of 16 mg), or per institutional standard. For subsequent episodes, use 4 mg QD prophylactic loperamide 30 minutes before subsequent dosing. Encourage patients to self-medicate with loperamide 2 mg should diarrhea recur (up to 2 mg every 4 h or after every unformed stool for a maximum daily dose of 16 mg), or per institutional standard.
 
• Monitor electrolyte levels closely and correct as appropriate.
 
• Administer IV fluids as clinically indicated.
 
• Upon presentation of Grade 3 diarrhea, exclude presence of active infections (e.g., Clostridium difficile). If present, treat infection(s) according to local guidelines.
 

Nausea and vomiting	
 
• Administer second-generation anti-emetics like palonosetron, ondansetron, or granisetron. If vomiting occurs within 15 minutes of
 

**Table 19 Guidelines for Management of Non-Hematologic Toxicities (cont.)**

Event		Action to Be Taken
		taking idasanutlin and all expelled tablets are still intact, another dose may be given and the second dose noted in the drug log. Otherwise, no replacement dose is to be given.
Dermatologic toxicity		Permanently discontinue rituximab in the event of Stevens-Johnson syndrome or toxic epidermal necrolysis.
Other non-hematologic toxicities (i.e., not described above), excluding alopecia, nausea, and vomiting	Grade 3 or 4	
For patients who have had no prior dose reductions:
 
 
Withhold study treatment.a
 
If improvement to Grade • 1 or baseline, resume obinutuzumab or rituximab at full dose and resume idasanutlin at a reduced dosea for current and subsequent cycles according to guidelines in Section 5.1.5 for current and subsequent cycles.
 
 
For patients who have had one prior dose reduction:
 
Grade 4 events
 
 
Permanently discontinue study treatment.
 
 
Grade 3 events
 
Withhold study treatment.a
 
 
If improvement to Grade • 1 or baseline, resume obinutuzumab or rituximab at full dose and idasanutlin at a reduced dose according to guidelines in Section 5.1.5 for current and subsequent cycles.
 
 
For patients who have had two prior dose reductions or for patients who reach the lowest dose level and no further dose reduction is applicable (See Section 5.1.1.5):
 
Permanently discontinue study treatment.

	Grade 2	
 
Withhold study treatment.a
 
If improvement to Grade • 1 or baseline, resume obinutuzumab or rituximab at full dose and idasanutlin at current dose
 

h = hour; IRR = infusion-related reaction; PML = progressive multifocal leukoencephalopathy; QD = once a day; TLS = tumor lysis syndrome; ULN = upper limit normal.

a Treatment delays apply to all events; dose modifications apply only to events that are considered to be related to any of the study treatment components. Toxicities that occur during the cycle and subside prior to the next cycle should not trigger the suggested dose modifications.

### 5.1.5.2 Toxicities during Maintenance Treatment

Table 20 provides guidelines for management of toxicities that occur during maintenance treatment.

**Table 20 Guidelines for Management of Toxicities That Occur during Maintenance Treatment**

Event	Action to Be Taken
Hematologic toxicity: Grade 3 or 4	

• Withhold study treatment.

• Administer myeloid growth factors for neutropenia as allowed according to institutional guidelines.

• If improvement to Grade • 2, resume obinutuzumab or rituximab at full dose and idasanutlin at reduced dose.

• If study treatment is withheld for >42 days, permanently discontinue.

Non-hematologic toxicity: Grade • 2	

• Withhold study treatment

• If improvement to Grade • 1 or baseline, administer obinutuzumab or rituximab at full dose and idasanutlin at reduced dose.

• If study treatment is withheld for >42 days, permanently discontinue.

## 5.2 SAFETY PARAMETERS AND DEFINITIONS

Safety assessments will consist of monitoring and recording adverse events, including serious adverse events and adverse events of special interest, performing protocol-specified safety laboratory assessments, measuring protocol-specified vital signs, and conducting other protocol-specified tests that are deemed critical to the safety evaluation of the study.

Certain types of events require immediate reporting to the Sponsor, as outlined in Section 5.4.

